2.2.1 Subgroup of interest

There is no planned subgroup of interest.

2.3 Patient disposition, demographics and other baseline characteristics

All data about patient demographics and baseline characteristics, including derived variables, will be summarized by cohort and overall with summary descriptive statistics on the Safety set. Continuous data will be summarized by n, mean, standard deviation, median, first and third quartiles, minimum and maximum. Categorical data will be presented by absolute and relative frequencies (n and %). P-values will also be displayed for both categorical and continuous variables, wherever required.

The number of patients in each analysis populations will be described and the reasons for excluding a patient from any particular population will be provided with the number of protocol violators for each criterion. The difference between cohorts with respect to protocol deviations and reasons for dropout will be examined by summarizing the protocol deviations by cohorts and overall on the all patients. Also, Major protocol deviations by cohorts and overall on the all patients.

Major protocol deviations are the deviations with Protocol Deviation IDs (DVSPID) as INCL01, INCL02, INCL03, INCL04, INCL05, EXCL02, EXCL03, EXCL04, EXCL05, EXCL06, EXCL07, EXCL15, EXCL16, EXCL19, COMD01, COMD02, COMD03, COMD04, COMD05, COMD06, COMD07, COMD08, COMD09, COMD11, COMD14, COMD16, COMD17, COMD18, COMD19, OTH08 and also patient's meeting the below criteria

• No secukinumab administration

- No valid PASI assessment after baseline
- Patient who didn't complete the study
- Patient's without Cw6 assessment.

Note:

- Prior use of prohibited PsO medication without the recommended wash-out period (PD: COMD01, COMD03, COMD05, COMD07, COMD09, COMD11, COMD16, COMD17, COMD18, COMD19).

- Concomitant use of PsO medication (PD: COMD02, COMD04, COMD06, COMD08, COMD10, COMD12, COMD14, COMD17, COMD18, COMD19).

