2.2 Analysis sets

The following analysis populations will be defined for statistical analysis.

- All patients: all patients who signed informed consent and entered in the study, including screen failure.
- Full Analysis Set (FAS): all enrolled patients (i.e. patients entered at week 0 visit 3).
- Safety: all enrolled patients included in the FAS population who were given at least one dose of study drug.
- Intent-to-treat (ITT): all patients included in the safety population with at least one post-baseline efficacy assessment and with the Cw6 assessment.
- Per-Protocol (PP): all patients included in the ITT population who completed the study without any major protocol violation.
- Core phase completers set: All patients who completed the Core phase visits (Week 24) are called core phase completer set.

The primary and secondary objectives will be evaluated on the ITT population. A supportive analysis will be done on the PP population.

All safety evaluations will be based on the safety set.

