2.3.1 Patient disposition

Summary of disposition for screening phase and study completion phase will be presented separately on All patients data.

For screening phase disposition, the number and percentage of patients screened, screen completed and discontinued will be summarized by cohorts and overall with reasons for discontinuation on All patients.

For patient's disposition, the number and percentage of patients screened, enrolled, completed and discontinued will be summarized by cohorts and overall in each study phase (i.e. Core and extension) with reasons for discontinuation on All patients.

Patient number and whether they completed or discontinued from the study at screening phase disposition and study completion core/extension phase disposition will be listed separately, with date of discontinuation and primary reason for discontinuation as applicable.

A brief summary of patients entered at each study visit will be provided.

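### SAP 2.3 tabulates major protocol deviations by cohort on a set that includes screen failures, each of whom counts as a major deviator as the list is written

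*SAP*

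**What the plan says.** SAP 2.2 defines All patients as "all patients who signed informed consent and entered in the study, including screen failure". The FAS is narrower: enrolled patients, meaning those who entered at week 0, visit 3.

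SAP 2.3 says that the difference between cohorts in protocol deviations and reasons for dropout will be "examined by summarizing the protocol deviations by cohorts and overall on the all patients". It then adds: "Also, Major protocol deviations by cohorts and overall on the all patients". Major deviations are a list of deviation IDs plus four criteria without an ID. Three of the four are "No secukinumab administration", "No valid PASI assessment after baseline" and "Patient who didn't complete the study". The fourth is a missing Cw6 assessment.

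SAP 2.3.1 plans a separate screening-phase disposition table. For the study phases it plans one table that also shows the screened and enrolled counts. Its wording is: "completed and discontinued will be summarized by cohorts and overall in each study phase (i.e. Core and extension) with reasons for discontinuation on All patients".

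SAP 1.1 sets the N for by-phase summaries of the extension as the patients who entered it. It gives no corresponding rule for the core phase.

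**The concern.** The cohorts are defined by genotype, not by randomisation. Protocol 9.2 therefore commits to examining whether they differ in deviations and in reasons for dropout. That check should describe what happened to patients who entered the study.

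On All patients, someone who failed screening has received no drug, has no PASI after baseline and has not completed the study. Nothing in SAP 2.3 restricts these criteria to enrolled patients, so the person is counted as a major deviator. Cw6 is typed at pre-screening (day -28), before eligibility is checked at visits 2 and 3. A typed screen failure therefore already carries a cohort label and enters the by-cohort columns.

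At stake is the meaning of one descriptive comparison. A difference between cohorts in screen failure would appear in the major-deviation total as if it were a difference in adherence to the protocol.

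**Working it through.** **Inputs from the documents.** Protocol 9.7 and SAP 3 give 365 evaluable patients (219 Cw6-positive, 146 Cw6-negative), 10% dropout at 16 weeks, and 406 enrolled.

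**The plan's own figure.** 365 / (1 - 0.10) = 405.6, rounded up to 406. This reproduces, so n = 406 is used as the enrolled number.

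**Inputs that must be assumed.** The documents give neither the number screened nor a deviation rate. I take a true any-major-deviation rate of m = 15% among enrolled patients, and let f, the share of All patients who fail screening, be 10%, 20% or 25%.

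**Formulas.** All patients = n / (1 - f). Each screen failure counts as a deviator, so:
- any-major-deviation rate on All patients = f + (1 - f) × m
- a row that can arise only after enrolment, with true rate r, becomes (1 - f) × r
- the core discontinuation rate, with true rate d, becomes (1 - f) × d if screen failures appear only in the separate screening table

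**Results** (r = 5% is also assumed; d = 10% is used for illustration)

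| f | All patients | Screen failures | Any major deviation (true 15%) | Post-enrolment row (true 5%) | Core discontinuation (true 10%) |
|---|---|---|---|---|---|
| 10% | 451 | 45 | 23.5% | 4.5% | 9.0% |
| 20% | 508 | 102 | 32.0% | 4.0% | 8.0% |
| 25% | 541 | 135 | 36.25% | 3.75% | 7.5% |

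Example for f = 20%: 0.20 + 0.80 × 0.15 = 0.32.

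The direction does not depend on these values. With any screen failures at all, the any-major total rises (as long as some enrolled patients have no major deviation) and the post-enrolment rows fall. Examples of such rows are OTH08 (continuing after PASI 50 was not reached at week 16) and the codes for prohibited drugs taken concomitantly.

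**Effect on the cohort comparison.** If both cohorts have the same true rate m, the displayed difference is (f1 - f2) × (1 - m). With m = 15% and assumed screen failure of 25% and 15%, the displayed rates are 36.25% and 27.75%. That is a difference of 0.10 × 0.85 = 8.5 points, produced by screening alone. If screen failure is equal in the two cohorts and the true rates are equal, no false difference arises.

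**One open point on discontinuation.** SAP 2.3.1 does not say whether a screen failure could also be counted as a core-phase discontinuation. If so, the rate would be inflated: at f = 20%, 0.20 + 0.80 × 0.10 = 28%.

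**The case against.** **Intent.** SAP 5.5 lists absence of secukinumab administration as excluding a patient from the ITT, safety and per-protocol sets, but not from the FAS. That fits a criterion written for patients already in the FAS, and protocol 5.5.1 records untreated patients on a separate screening disposition form. This is a fair hint of intent. It does not override SAP 2.3, which names All patients for both summaries and does not restrict the criteria.

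**Visibility.** Screening disposition is tabulated separately by cohort, and SAP 2.3 reports violators for each criterion, so a careful reader could trace the inflation to its rows. That is so, but the any-major total and the cohort comparison drawn from it would still be wrong as printed.

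**Drop-out.** A reader might infer that observed drop-out could not be checked against the 10% in the sample size. The documents do not support that. SAP 2.3.1 puts the enrolled and discontinued counts in the same table, so the rate on enrolled patients is one division away. The 10% also refers to week 16, whereas the core phase ends at week 24, so the core-phase percentage is not its direct comparator even on the FAS.

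**Unequal screen failure.** Patients and investigators are blinded to Cw6, which makes a large difference between cohorts less likely. It is not excluded. Enrolment stops in one cohort when its target is reached (at most 244 Cw6-positive), and patients typed after that could become screen failures in that cohort only. The documents do not say how they would be recorded.

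**Conclusion.** The point holds as a minor one. On the text of SAP 2.2 and 2.3, the any-major-deviation total and three criterion rows are inflated by screen failures, rows that arise only after enrolment are diluted, and the cohort comparison of deviations absorbs any difference in screen failure. The size rests wholly on assumptions: about 23.5% to 36% in place of an assumed 15%, for screen failure of 10% to 25%.

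Two wider readings should be resisted. One is that all deviation rates are inflated. The three criteria belong only to the major list, and some rows of that list move the other way. The other is that the trial's conclusions are affected. Screen failures are outside the FAS and therefore outside the safety, ITT and per-protocol sets. SAP 2.3 and 2.3.1 specify no test on these tables, and no efficacy, per-protocol or safety estimate changes.

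**What to change.** In SAP 2.3, summarise protocol deviations and major protocol deviations on the FAS, by cohort and overall. In SAP 2.3.1, put core-phase completion and discontinuation with reasons on the FAS as well. State the core-phase N explicitly, as SAP 1.1 does for the extension. Keep All patients for the screening-phase disposition and for the counts of patients excluded from each analysis set.

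The cost is a change of analysis set in two SAP sections, one sentence on the core-phase N, and the matching table shells. No new data are needed.

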COMD01	Use of Prohibited medication (Ustekinumab as prior psoriasis therapy)	EXCLUDE FROM PP	4
COMD03	Use of Prohibited medication (Alefacept as prior psoriasis therapy)	EXCLUDE FROM PP	4
COMD05	Use of Prohibited medication (Etanercept as Prior Psoriasis Therapy)	EXCLUDE FROM PP	4
COMD07	Use of Prohibited medication (Adalimumab as Prior Psoriasis Therapy)	EXCLUDE FROM PP	4
COMD09	Use of Prohibited medication (Infliximab as Prior Psoriasis Therapy)	EXCLUDE FROM PP	4
COMD11	Use of Prohibited medication (Golimumab as Prior Psoriasis Therapy)	EXCLUDE FROM PP	4
COMD16	Use of Prohibited medication (Phototherapy as Prior Psoriasis Therapy)	EXCLUDE FROM PP	4
COMD18	Use of Prohibited medication (Other systemic psoriasis treatments)	EXCLUDE FROM PP	4
COMD19	Use of Prohibited medication (Topical treatment that is likely to impact signs and symptoms of psoriasis)	EXCLUDE FROM PP	4
COMD02	Use of Prohibited medication (Ustekinumab taken concomitantly)	EXCLUDE FROM PP	4
COMD04	Use of Prohibited medication (Alefacept taken concomitantly)	EXCLUDE FROM PP	4
COMD06	Use of Prohibited medication (Etanercept taken Concomitantly)	EXCLUDE FROM PP	4
COMD08	Use of Prohibited medication (Adalimumab taken concomitantly)	EXCLUDE FROM PP	4
COMD14	Use of Prohibited medication (Phototherapy taken concomitantly)	EXCLUDE FROM PP	4
COMD17	Use of Prohibited medication (Other systemic immunomodulating treatments)	EXCLUDE FROM PP	4
OTHER	No secukinumab administration	EXCLUDE FROM ITT SAF PP	2
OTHER	No valid PASI assessment after baseline	EXCLUDE FROM ITT PP	4

Deviation ID	Description of Deviation (DVTERM)	Exclusion in Analyses	Severity code
OTHER	Patient who didn't complete the study	EXCLUDE FROM PP	4
OTHER	Patient's without Cw6 assessment	EXCLUDE FROM ITT PP	5

Table 2Subject Classification rules

Analysis set	PD Population Codes that cause patient to be excluded	Non-PD criteria that cause a patient to be excluded
FAS	1,3	
ТТ	1,2, 4, 5	NA
Per-protocol	1,2,4, 5, 6	Not in ITT
Safety	1,2, 3, 6	No study drug taken

6 Reference

Expert panel on detection, evaluation, and treatment of high blood cholesterol in adults. Executive summary of the third report of the national cholesterol education program (NCEP) expert panel on detection, evaluation and treatment of high blood cholesterol in adults (Adult treatment Panel III). JAMA 2001; 285:2486-97.

Newcombe, R. G. "Interval estimation for the difference between independent proportions: comparison of eleven methods", Stat Med;17(8):857-72.

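### COMD10 and COMD12 are named in SAP 2.3 as concomitant psoriasis-medication deviations but are missing from its major-deviation list and from the per-protocol exclusion table in 5.5

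*SAP*

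**What the plan says.** SAP 2.2 defines the PP set as "all patients included in the ITT population who completed the study without any major protocol violation". SAP 2.3 then lists the codes that count as major. The COMD part of that list ends "COMD08, COMD09, COMD11, COMD14, COMD16, COMD17, COMD18, COMD19, OTH08", so it goes from COMD09 to COMD11 to COMD14.

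The note below that list sorts the medication codes into two groups:

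- Prior use: "Prior use of prohibited PsO medication without the recommended wash-out period (PD: COMD01, COMD03, COMD05, COMD07, COMD09, COMD11, COMD16, COMD17, COMD18, COMD19".
- Concomitant use: "Concomitant use of PsO medication (PD: COMD02, COMD04, COMD06, COMD08, COMD10, COMD12, COMD14, COMD17, COMD18, COMD19".

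SAP 5.5 Table 1 gives each excluding deviation a description, the sets it excludes from, and a severity code. Its last concomitant anti-TNF row is COMD08, "Use of Prohibited medication (Adalimumab taken concomitantly". Infliximab and golimumab appear only as earlier therapy: COMD09, "Use of Prohibited medication (Infliximab as Prior Psoriasis Therapy", and COMD11, "Use of Prohibited medication (Golimumab as Prior Psoriasis Therapy". There is no row for COMD10 or COMD12.

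SAP 2.5.4 plans PP analyses of the primary variable under LOCF, NRI and observed data (which the SAP calls prevalence). SAP 2.3 plans a summary of major deviations by cohort.

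**The concern.** A code that the SAP itself classes as concomitant use of psoriasis medication should be treated like the others in its group, or the SAP should say why it is not. As written, eight concomitant codes remove a patient from PP and two do not. The listed rule therefore gives different results for the same kind of deviation.

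Two outputs are at stake. One is the PP analysis of PASI 90 at week 16. The primary question is tested against a 12% non-inferiority margin, so a cleanly defined PP set is useful supporting evidence. The other is the summary of major deviations, which would leave these two codes out.

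**Working it through.** The plan gives no figure of its own to reproduce here. The check compares lists of codes.

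**Inputs (COMD numbers only)**

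| Source | Codes | Count |
|---|---|---|
| SAP 2.3 note, prior use | 01, 03, 05, 07, 09, 11, 16, 17, 18, 19 | 10 |
| SAP 2.3 note, concomitant use | 02, 04, 06, 08, 10, 12, 14, 17, 18, 19 | 10 |
| SAP 2.3 major-deviation list | 01 to 09, 11, 14, 16, 17, 18, 19 | 15 |
| SAP 5.5 Table 1 | the same codes as the major-deviation list | 15 |

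**Comparison**

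1. Codes in both groups of the note: 17, 18, 19, so 3.
2. Distinct codes in the note: 10 + 10 − 3 = 17.
3. Major-deviation list against Table 1: no difference.
4. Prior-use codes missing from either list: none (10 of 10 carried).
5. Concomitant-use codes missing from either list: COMD10 and COMD12 (8 of 10 carried).
6. Total: 17 − 15 = 2. Adding both codes gives 15 + 2 = 17 in each list, with nothing left over.

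**What the two codes probably are.** Table 1 describes four complete pairs: 01/02 ustekinumab, 03/04 alefacept, 05/06 etanercept and 07/08 adalimumab. In each, the odd code is prior use and the next even code is concomitant use. COMD09 is prior infliximab and COMD11 is prior golimumab, so 10 and 12 would be their concomitant partners. The phototherapy codes (16 prior, 14 concomitant) break the pattern, so this remains an inference. COMD17, "Use of Prohibited medication (Other systemic immunomodulating treatments", does not clearly cover the two drugs. Protocol Table 5-1 puts them in a separate group of biological agents.

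**Can such a patient reach PP?** PP requires completing the study.

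- Protocol 5.5.9 lists use of a prohibited treatment among the reasons for which study drug must be stopped.
- Protocol 5.5.8 lets a patient give up the prohibited drug and stay in the study.
- Protocol section 6 asks patients who stop study drug to keep returning for assessments, and the glossary separates stopping treatment from leaving the study.

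So completion is possible, and no listed COMD code would then remove the patient from PP.

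**Side check: exclusion 6 on IV or intramuscular steroids.** It looks back 2 weeks from screening; Table 5-1 asks for 4 weeks (28 days) before day 1.

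| Screening taken as | Look-back before day 1 | Against 28 days |
|---|---|---|
| Visit 2 on day −7 | 7 + 14 = 21 days | 7 days looser |
| Visit 2 on day −14 | 14 + 14 = 28 days | equal |
| Pre-screening, day −28 | 28 + 14 = 42 days | 14 days stricter |

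**The case against.** The strongest reply is that the consequence is conditional. SAP 2.3 summarises all deviations as well as the major ones, so a code in the note but outside the major list is not a contradiction in itself. Neither code is described. Most patients who take a prohibited biologic may stop study drug and leave, and non-completion already removes them from PP. The codes may have been left out on purpose, for example because no case occurred. All of this limits the size of the point. It does not explain why two of ten concomitant codes are treated differently, and the SAP gives no reason.

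Three stronger readings are tempting, and the documents do not support them.

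- **That the ITT analysis is certainly untouched.** The ITT definition in SAP 2.2 has no medication exclusion, and Table 1 marks the COMD codes as PP only. But those codes carry severity code 4, and Table 2 of SAP 5.5 lists code 4 among the ITT exclusions. The two tables disagree, so neither can be cited alone.
- **That exclusion 6 is looser than Table 5-1.** That holds only if screening means visit 2 later than day −14. Protocol 6.1 and SAP Table 2.1 also use the word for visit 1 or for the period that starts on day −28. The defensible point is ambiguity.
- **That exclusion 5 conflicts with the 6-month washout for alefacept, briakinumab and efalizumab.** Exclusion 5 concerns biologics given for psoriasis and has no washout clause, so it governs. The Table 5-1 row is not limited by indication, and the two can coexist.

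**Conclusion.** The omission is real and exact: COMD10 and COMD12 are the only codes in the SAP 2.3 note that are absent from both the major-deviation list and Table 1. Under the listed rule, a patient with either code who completes the study stays in PP.

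The point is minor. It concerns a supportive set, used with three missing-data approaches for the primary variable, and one deviation summary. The number of patients is unknown and may be zero, so no bias in any result can be claimed. The count of codes rests on no assumption. The drug names rest on the numbering pattern, and the consequence rests on at least one such patient completing. A reader might infer that concomitant infliximab or golimumab users will be counted as protocol-compliant. The documents show only that the listed codes would not exclude them.

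**What to change.** 1. Add COMD10 and COMD12 to the major-deviation list in SAP 2.3 and to SAP 5.5 Table 1, each with a description, as exclusions from PP only. If they were left out on purpose, say so in one sentence.
2. Before giving them a severity code, reconcile Tables 1 and 2 of SAP 5.5. Code 4 is used in Table 1 both for PP-only deviations and for the row on having no valid PASI after baseline, which excludes from ITT as well. A separate code for PP-only deviations, absent from the ITT row of Table 2, would keep the two new codes from removing patients from ITT.
3. Optional: state in exclusion 6 which visit screening refers to, or count from day 1 as exclusion 2 does, and align EXCL06 in the SAP.

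Items 1 and 2 are edits to SAP lists and need no new data, visit or eCRF item. Item 3 changes the protocol, so under Protocol 11.1 it needs a written, approved amendment. It is worth doing only alongside other changes.

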2.3.1 Patient disposition

Summary of disposition for screening phase and study completion phase will be presented separately on All patients data.

For screening phase disposition, the number and percentage of patients screened, screen completed and discontinued will be summarized by cohorts and overall with reasons for discontinuation on All patients.

For patient's disposition, the number and percentage of patients screened, enrolled, completed and discontinued will be summarized by cohorts and overall in each study phase (i.e. Core and extension) with reasons for discontinuation on All patients.

Patient number and whether they completed or discontinued from the study at screening phase disposition and study completion core/extension phase disposition will be listed separately, with date of discontinuation and primary reason for discontinuation as applicable.

A brief summary of patients entered at each study visit will be provided.

2.3.2 Patient demographic and other baseline characteristics

Summary statistics n, mean, median, standard deviation, minimum, maximum, first and third quartiles will be presented for continuous variables for each cohort and overall on the Safety set. The number and percentage of patients in each category will be presented for categorical variables for each cohort and overall on the Safety set.

The following demographic and baseline variables will be summarized:

Demographic variables:

Continuous variables:

- Age (years)
- Height (cm)
- Weight (kg)
- Waist (cm)
- BMI (kg/m^2) will be calculate as (body weight in kilograms) / (height in meters)²

Categorical variables:

- Age categories (<65, >=65)
- Sex (Male, Female)
- BMI categories (<25 vs >=25)
- Race (Caucasian, Black, Asian, Native American, Pacific Islander, Unknown, Other)
- Ethnicity (Hispanic or Latino, Chinese, Japanese, Indian, Mixed Ethnicity, Other)
- Geographical region (north vs south/central)
- Smoking status at baseline
 - Never
 - Current
 - Former

Baseline disease characteristics variables:

Continuous variables:

- Baseline PASI score
- Baseline IGA mod 2011 score
- Age at diagnosis of psoriasis (years)
- Time since first diagnosis of psoriasis (years) (which is derived as date of baseline visit-date of first diagnosis of psoriasis)
- Time since first diagnosis of psoriatic arthritis (years) (which is derived as date of baseline visit-date of first diagnosis of psoriatic arthritis)

Categorical variables:

- Type of psoriasis history at diagnosis
 - Plaque type psoriasis
 - Nail psoriasis
 - Scalp psoriasis
- Number of patients with psoriatic arthritis
 - Type of psoriatic arthritis
 - Polyarticular
 - Monoarticular
 - Axial
 - Enthesitis
 - Dactylitis
- Quantiferon TB-Gold test
 - Negative
 - Positive
 - Indeterminate
- PPD test
 - Negative

- Positive
- Indeterminate
- TNFα 308 polymorphism
 - Heterozygous
 - Homozygous
- Metabolic syndrome
 - Yes
 - No

Definition of metabolic syndrome

Metabolic syndrome is defined as the presence of at least 3 of the 5 following criteria(Expert Panel JAMA 2001) :

- Increased waist circumference (≥ 102 cm for men, ≥ 88 cm for women).
- elevated triglycerides ($\geq 150 \text{ mg/dl}$).
- Reduced high-density lipoprotein (HDL) cholesterol ($\leq 40 \text{ mg/dl}$ in men and $\leq 50 \text{ mg/dl}$ in women).
- Elevated blood pressure (≥ 130 mmHg systolic and ≥ 85 mmHg diastolic or ongoing treatment for hypertension).
- Elevated glucose (≥100 mg/dl or ongoing treatment for elevated glucose)

In order to interpret results adequately, the homogeneity of patient distribution between cohorts will be tested on selected baseline demographics and anamnestic variables (e.g. for gender, age, race, ethnicity, BMI, baseline PASI, baseline IGA, $TNF\alpha$ - 308 polymorphism, metabolic syndrome, smoking).

Categorical variables – as race, ethnicity, geographical region and type of PsA will be analyzed by Cochran-Mantel-Haenszel, while the remaining variables listed in the table below will be analyzed by means of a regression logistic model.

Continuous variables will be analyzed by means of an ANCOVA model corrected as indicated in the table below.

Number of patients with presence of PsA will be analyzed by means of Chi Square test.

Moreover, differences between cohorts in BMI, height, weight, waist, geographical distribution, type of psoriasis, age at PsO diagnosis, time since PsO diagnosis, concomitant PsA, type of PsA, time since PsA diagnosis, quantiferon TB-Gold, PPD test will be also explored. Variables reported in the table below will be included as covariates in the explanatory analysis model.

Normality data distribution will be assessed by means of Shapiro-Wilk test and with graphical methods (if possible). In case of non-normality, a non-parametric test will be used, if feasible.

Variable analyzed	Covariates/stratification factors
Age/ age group	Sex

Sex	Age
BMI/height/weight/waist/ BMI categories	Age, sex
Type of PsO (other than plaque)/ Time since PsO diagnosis/ age at PsO diagnosis/ presence of PsA/ time since PsA diagnosis/ metabolic syndrome	Age, sex, waist
PASI at baseline / IGA at baseline	Age, sex, waist, type of PsO, time since PsO diagnosis, presence of PsA
Race/ethnicity/geographical region/ Type of PsA	none
Smoking status	Age, sex
TNF-alpha polimorphism / quantiferon / PPD	Age

Medical history

Any condition entered as medical history or current medical conditions at baseline will be coded using the MedDRA dictionary version 18.1 or latest available. They will be summarized by system organ class (SOC) and preferred term (PT) of the MedDRA dictionary on the Safety set and will be presented by cohorts and overall.

Differences in total number of comorbidities (i.e., all medical histories with categories General) between cohorts will be assessed by means of a Poisson model taking into account the following factors: age (tertiles), sex and time since PsO diagnosis. In this case, the total number of medical histories are to be considered for all patients by cohort. Additionally Poisson analyses will be done for total number of comorbidities including PsA category along with General category of MH will also be performed.

